## 12. Data Review Committees

There will be a Publications Committee. Applicable information regarding Publication policy is described in the Publication Plan, separate document from this Protocol.

# 13. Statistical design and methods

The following statistical analysis plan of the data will be carried out:

The variables analyzed will be those collected in the subject registry corresponding to the different protocols of the procedure, intervention data, complications, follow-up and long-term results in these subjects. In the Method section there is a list of variables of interest.

Recurrence of AF will be defined as a clinically diagnosed episode of AF and accordingly documented (on ECG, Holter monitor with a duration of at least 30 seconds or implantable devices or event recording systems).

It is expected to carry out 3 analyses of the primary and secondary objectives described in the Clinical Investigation Plan:

- 1. At the end of the first year of enrollment
- 2. At the end of the second year of enrollment
- 3. At the end of follow-up

On the other hand, there will be 4 analyses of additional proposals throughout the study (see Appendix B: Publications Plan)

- Two analyses at the end of enrollment.
- Two analyses at the end of follow-up.

Each of the variables of interest will be described univariantly and individually.

Crosses of variables will also be carried out to describe each one of the clinical strata of interest.

When it is possible and of interest for the investigators, statistical comparisons between strata will be carried out through statistical tests.

Specific statistical models to respond to the interests of the investigators will be proposed, such as comparison of the procedures or comparison of subject strata.

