# 5. Study objectives and endpoints

## 5.1. Objectives

#### **5.1.1.** Primary Objective

To evaluate the efficacy of the cryoablation procedure at 12 months, defined as the absence of recurrences of atrial fibrillation.

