## 13.1. Analysis of clinical data

It is expected to include approximately 1000 subjects enrolled at approximately 30 Spanish sites, with an enrollment period of 2 years and a follow-up period of one year from the time of enrollment of each subject. The subjects analyzed will be the ones included in the RECABA study database: "Spanish Registry of Cryoballoon Ablation". The variables analyzed will be those mentioned previously with the intention of adequately describing the activity of the clinical sites, the procedures used and the diseases treated in accordance with standard clinical practice.

All the data are anonymized in origin so that it is not possible to identify the subjects.

The collection of data will be prospective from the time of enrollment.

The database will be received codified and debugged, and the allocation of the lost values that have been decided previously.

The basic report at the end of enrollment and at the end of the follow-up period will consist of: The quantitative variables are expressed as mean, median, typical deviation and interquartile range depending on which is most suitable for the distribution of values. The differences between groups in relation to the quantitative variables will be evaluated through the student t test for independent samples or the analysis of variance (depending on the number of groups compared) and between variables through the student t test for related samples or the analysis of variance of repeated measures, as applicable. To analyze the relationships between categorical variables the chi-squared test ( $\chi^2$ ) and the Fisher's exact test will be used. The differences of proportions will be assessed through the homogeneity test  $\chi^2$ . To assess the relationships between the quantitative variables the Pearson or Spearman r correlation will be used, as appropriate.

The intermediate statistical reports proposed by the investigators will depend on the hypotheses suggested by the investigator. They will include at least a descriptive analysis such as the one described previously. In addition, the appropriate models to respond to the hypotheses proposed will be estimated, which can include techniques of the style of exploratory factor analysis, analysis of multiple contingency, analysis of logistical regression, analysis of conglomerates or analysis of multifactorial variance.

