### **Treatment of missing values**

The statistical analysis process assumes the correct monitoring of the data entry through the electronic data collection notebook. During the data analysis phase, no queries should be made to fill in missing information or missing values.

However, during the analysis process, missing and missing values will be identified for later treatment with the research team. Extreme and out-of-range values will also be identified for later review by the research team. The necessary corrections obtained from the identification of out-of-range values or missing information and reviewed by the patient's clinical manager will be entered into the database for subsequent treatment in subsequent re-analyses.

The initial data treatment strategy will be to assume a non-response as a completely random missing value (MCAR) and the treatment of missing values will be isolated by variable. If it is required to relate several variables in an analysis, the treatment will be "according to the pair" of variables considered (pairwise) to minimize the impact of the lost information on the estimates obtained.

In the cases in which the analysis of several consecutive measurements is carried out or the passage of time is valued, the carrying over of the last value obtained on subsequent measurements will be assumed. For example, if a subject has not suffered an event or there is no information on this aspect (missing value) at the time of closing the database, it will be assumed that the subject's status is the same as the last measurement with valid data.

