### **Statistical models**

In order to conclude on the primary objective of the study, the number and percentage of cases with absence of atrial fibrillation recurrences will be calculated after 12 months of follow-up, after the cryoablation procedure. The scientific coordinators of the study will have to determine the closing date of the database so that it has been possible to collect information from 12 months of follow-up of a sufficiently large number of patients.

The protocol defines AF recurrence as a clinically diagnosed and documented episode of AF (using ECG, Holter monitor with a duration of at least 30 seconds, or using implantable devices

or event monitoring systems). The information necessary to determine the existence of a recurrence of AF will be extracted from the Follow-up and Adverse Events tables.

The existence of differences between patients with and without recurrence in clinical variables and patient follow-up will be explored. Student's t statistics (for continuous variables) and  $\chi^2$  (for categorical variables) will be used. If there are appreciable differences between the groups of patients in the clinical variables, logistic regression models will be proposed to study the multivariate effect of the variables and assess their predictive capacity.

The waiting times until the moment of recurrence of AF will be described using survival models (survival tables and Kaplan-Meier) and the existence of variables capable of predicting the differences between both groups of patients will be explored.

The necessary statistical analyzes will be approached to verify the secondary objectives based on the variables designated by the study coordinators.

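### The 12-month primary objective is scheduled for analysis at the end of enrolment year 1, when no subject can be past 12 months, and the SAP does not match that schedule

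*Protocol*

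**What the plan says.** Protocol section 5.1.1 gives the primary objective: "To evaluate the efficacy of the cryoablation procedure at 12 months, defined as the absence of recurrences of atrial fibrillation". Section 13 then states: "It is expected to carry out 3 analyses of the primary and secondary objectives described in the Clinical Investigation Plan". The first of the three is placed "At the end of the first year of enrollment", the second a year later, and the third when follow-up ends. Nothing limits the first to particular objectives.

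Section 13.1 describes the content of a report at two of these times: "The basic report at the end of enrollment and at the end of the follow-up period will consist of". It does not mention a year-1 report.

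The SAP, under Statistical models, says that "the number and percentage of cases with absence of atrial fibrillation recurrences will be calculated after 12 months of follow-up", counted after the procedure. It leaves the database closing date to the scientific coordinators, to be set so that it is possible to "collect information from 12 months of follow-up of a sufficiently large number of patients". No number is given, and the year-1 and year-2 analyses are not mentioned.

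The SAP's Treatment of missing values carries the last value forward "In the cases in which the analysis of several consecutive measurements is carried out or the passage of time is valued". Its example is a subject with no event, or no information, when the database closes: "it will be assumed that the subject's status is the same as the last measurement with valid data".

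**The concern.** Read literally, section 13 asks for a result on a 12-month outcome at a date when nobody has more than 12 months of follow-up, while the SAP ties that result to completed follow-up. If a figure is produced anyway, at year 1 or year 2, its value depends on a denominator that neither document states. The carry-forward example describes the situation of a subject who has not yet reached 12 months. Counting such subjects as recurrence-free would push the percentage up.

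The interim figures are not idle. Protocol section 15.8.1 gives an intermediate analysis that departs from the study's objectives as an example of grounds for early termination, without a numerical criterion.

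**Working it through.** **Inputs from the documents.** About 1000 subjects enrolled from May 2016 to May 2018, 24 months (section 8.1). One year of follow-up per subject (section 13.1). Annual visit at 12 months ± 28 days, that is ± 0.92 months, and a 3-month blanking period (section 9.1). The stated duration reproduces: 2 + 1 = 3 years. No precision or power inputs stand behind the 1000.

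**Assumptions, not in the documents.** Even accrual, procedure on the day of enrolment, no drop-out. Three other accrual patterns are used for the range: rate rising linearly from zero; a 6-month ramp, then constant; rate falling from 1.5 to 0.5 times the average.

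**Step 1. Who has 12 months at each analysis.** The number with 12 months at calendar month T is the number enrolled by T − 12. The number with a closed window is the number enrolled by T − 12.92.

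| Analysis | Enrolled | Full 12 months | Window closed |
|---|---|---|---|
| 1 (month 12) | 500 | 0 | 0 |
| 2 (month 24) | 1000 | 1000 × 12/24 = 500 (50%) | 1000 × 11.08/24 = 462 (46%) |
| 3 (month 36) | 1000 | 1000 | 1000 × 23.08/24 = 962 (96%) |

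- Analysis 1: the zeros do not depend on the accrual pattern. A visit 28 days early is possible for 0.92/12 = 7.7% of those enrolled, about 38 of 500. Under the other patterns this is 0.6%, 0.8% and 9.1%. Under even accrual, a 14-day lag from enrolment to procedure cuts the 38 to 19, and a 30-day lag to zero.
- Analysis 2, other patterns: 25%, 43% and 63% have a full 12 months; 21%, 38% and 59% have a closed window. With even accrual and a lag of 1, 2 or 3 months before the procedure, 45.8%, 41.7% and 37.5% have a full 12 months.
- Analysis 3: a data cut exactly at month 36 still leaves about 38 windows open.

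**Step 2. Illustration of carry-forward applied to everyone enrolled.** Assume no countable recurrence in months 0-3 and a constant hazard in months 3-12 that gives a true 12-month recurrence-free proportion S.

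- Month 12, follow-up uniform on 0-12 months: apparent proportion = 0.25 + 0.75 × (1 − S)/(−ln S). For S = 0.75: 0.25 + 0.75 × 0.25/0.2877 = 0.902.
- Month 24, half complete and half as above: 0.5 × 0.75 + 0.5 × 0.902 = 0.826.
- S = 0.60 gives 0.837 and 0.719. S = 0.85 gives 0.942 and 0.896.
- Other accrual patterns at S = 0.75: 0.89-0.95 at month 12 and 0.80-0.88 at month 24.

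**Step 3. A closed-window denominator at analysis 2.** With 462 subjects and S = 0.75, the 95% half-width is 1.96 × √(0.75 × 0.25/462) = 0.039, against 0.027 with 1000.

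Membership must not depend on whether a recurrence has already been reported. Recurrences go on the adverse event form when they occur (Table 1 and section 11.2). The open-window subjects would have about 500 × (1 − 0.902) + 38.3 × 0.25 = 58.7 recurrences. Adding them gives 346.3/(461.7 + 58.7) = 0.665, where 346.3/461.7 = 0.750.

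**The case against.** The strongest reply is that the SAP already prevents a premature percentage. It calculates after 12 months of follow-up and chooses the closing date accordingly, and section 13 speaks only of an expectation covering primary and secondary objectives together. Profile, acute isolation, complications and procedure-stage resource use can all be analysed at year 1. That is a plausible account of the intent. Section 13 nevertheless names the primary objective without restriction, and the SAP does not refer to its dates.

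Three stronger readings are tempting, and the documents do not support them:

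- *No year-1 figure could exist at all.* The visit window runs from 28 days before the anniversary, so a few subjects could have an in-window annual visit by then. What holds is that none is past 12 months and no window has closed.
- *Section 13.1 contradicts section 13 by allowing only two reports.* It describes a basic report at two times and does not exclude others. It is silent on year 1, which is an ambiguity.
- *The plan as written inflates success to 90%.* The SAP does not expressly tie its carry-forward example to the primary percentage. Those figures show what would follow if the example were used that way.

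It can also be said that the SAP plans Kaplan-Meier analysis, which accommodates incomplete follow-up. It does so for time to recurrence, not for the primary percentage, and states no censoring rule. If event-free time were recorded only at the annual visit and subjects were censored at their last recorded visit, while recurrences are entered as they occur, an early curve would be biased downward. That depends on implementation.

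**Conclusion.** The mismatch is real and minor. The statement that no subject is past 12 months at analysis 1 follows from the calendar alone. The shares of about 8% with a possible early visit at analysis 1 (1-9% under other accrual patterns) and about half with 12 months at analysis 2 (25-63%) rest on assumed accrual, and on no delay before the procedure. Whether half is enough for the SAP cannot be judged, because it gives no number. The 90% and 83% are illustrations that also need an assumed true 75%, a constant hazard and a use of carry-forward that the SAP does not prescribe.

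The main effect is on the interim figures. It would be too generous to say that it must stop there: the SAP's closing date requires only enough patients with 12 months, so a final cut made before all windows close would be affected in the same way. A reader might also infer that the sample size or the final result is unsound. Nothing here supports that, provided the final cut follows the last window.

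**What to change.** 1. **Protocol sections 13 and 13.1.** State that analysis 1 covers only subject profile, acute isolation, procedure and procedure-stage resource data, and complications. List the same three reports in both sections.
2. **SAP, Statistical models.** State that any 12-month percentage uses as denominator all subjects whose 12-month window (+28 days) has closed by the data cut, whether or not a recurrence was already reported. Count the window from the procedure, as the SAP does; section 13.1 counts follow-up from enrolment. Give the number with unknown status. Show the percentage among those with known status, with bounds that count all unknowns first as recurrence and then as recurrence-free.
3. **SAP, Treatment of missing values.** State that carry-forward is not used to count subjects without 12-month information as recurrence-free.
4. **Definitive figure.** Report it after the last subject's window closes. Any interim Kaplan-Meier curve must not censor at the last recorded visit while recurrences are reported as they occur.

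Cost: wording in two protocol sections and two SAP paragraphs, with no new visits, data fields or subjects. There would be no 12-month figure at year 1. The year-2 denominator would be smaller: about 462 of 1000 under even accrual with no procedure lag, with a 95% half-width of about 3.9 points at 75%.

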## 13.1. Analysis of clinical data

It is expected to include approximately 1000 subjects enrolled at approximately 30 Spanish sites, with an enrollment period of 2 years and a follow-up period of one year from the time of enrollment of each subject. The subjects analyzed will be the ones included in the RECABA study database: "Spanish Registry of Cryoballoon Ablation". The variables analyzed will be those mentioned previously with the intention of adequately describing the activity of the clinical sites, the procedures used and the diseases treated in accordance with standard clinical practice.

All the data are anonymized in origin so that it is not possible to identify the subjects.

The collection of data will be prospective from the time of enrollment.

The database will be received codified and debugged, and the allocation of the lost values that have been decided previously.

The basic report at the end of enrollment and at the end of the follow-up period will consist of: The quantitative variables are expressed as mean, median, typical deviation and interquartile range depending on which is most suitable for the distribution of values. The differences between groups in relation to the quantitative variables will be evaluated through the student t test for independent samples or the analysis of variance (depending on the number of groups compared) and between variables through the student t test for related samples or the analysis of variance of repeated measures, as applicable. To analyze the relationships between categorical variables the chi-squared test ( $\chi^2$ ) and the Fisher's exact test will be used. The differences of proportions will be assessed through the homogeneity test  $\chi^2$ . To assess the relationships between the quantitative variables the Pearson or Spearman r correlation will be used, as appropriate.

The intermediate statistical reports proposed by the investigators will depend on the hypotheses suggested by the investigator. They will include at least a descriptive analysis such as the one described previously. In addition, the appropriate models to respond to the hypotheses proposed will be estimated, which can include techniques of the style of exploratory factor analysis, analysis of multiple contingency, analysis of logistical regression, analysis of conglomerates or analysis of multifactorial variance.

A nominal significance of a=0.05 will be assumed for a result to be considered statistically significant. The statistical analysis will be achieved using the statistical packet SPSS 20.0.

#### 14. Ethics

## 14.1. Statement(s) of compliance

The study will be conducted in compliance with the most recent version of the Declaration of Helsinki, Spanish laws and regulations (Royal Decree 1090/2015, Royal Decree 1616/2009, Order SAS/3470/2009 of 16 December), including data protection laws mentioned in previous section, the clinical investigation contract and the Clinical Investigation Plan.

All the principles of the Declaration of Helsinki have been implemented in this observational study through the signature process of the Data Release Form, approval by the Clinical Research Ethics Committee, training in the study, registration of the observational study, publication policy, etc.

This observational study does not require the authorization of the Spanish Agency of Medicines and Medical Devices (AEMPS), as stipulated in Royal Decrees 1090/2015 and 1616/2009 since it is a clinical investigation with medical devices which already hold the CE mark and these are used in accordance with the clinical purpose taken into account in the pertinent procedure of evaluation of compliance.

Since it is an observational study where standard clinical practice is being followed with products with CE mark in accordance with local legislation, the evaluation and approval of the observational study by a single Ethics Committee (EC) of one of the participating sites is considered sufficient. Once the reference

Version 1.0 11/APR/2016 EC approval has been obtained, the EC from each participating site will assess whether it is necessary to evaluate the local aspects of the observational study. Any additional requirements imposed by the EC shall be followed. If any action is taken by the EC with respect to the investigation, that information will be forwarded to the sponsor.

# 15. Study Administration

## 15.2. Data Management

The data from the CRF will be stored in a secure, password-protected database. The data will be reviewed through manual and scheduled data edit checks. The discrepancies will be raised at the sites to proceed to their resolution through queries. At the end of the study, the data will be stored as a frozen data set and Medtronic will store them.

# 15.3. Direct access to source data/documents

Medtronic may conduct audits at participating investigational sites. The purpose of an audit is to verify that the activities related to the study are performed properly. The regulating authority may also carry out inspections in the participating research sites. All announcements of inspections by the regulating authority must be reported as soon as possible to the Sponsor.

The investigator and/or the institution must allow the Sponsor and designated representatives by the Sponsor and the regulatory organizations direct access to the data and source documents, taking into consideration all of the restrictions of local laws, to carry out monitoring related to the study, audits, and regulatory inspections.

# 15.4. Confidentiality

Personal data will be processed at all times with due confidentiality and privacy, and in accordance with the applicable regulations on data protection and privacy, in particular in compliance with Spanish Organic Law 15/1999, of December 13, 1999, on personal data protection and with its secondary legislation, including Royal Decree 1720/2007, of December 21, 2007, Regulation implementing Organic Law 15/1999 and Law 41/2002, of November 12, 2002, on basic regulations for subject autonomy.

#### 15.5. CIP amendments

Medtronic will send all significant amendments to the Clinical Investigation Plan, including justification for these amendments, to the investigators and to the corresponding ECs for approval.

Amendments to the Clinical Investigation Plan must be agreed between the Sponsor and the Scientific Committee.

#### 15.6. Record Retention

#### 15.6.1. Study records

The records are subject to inspection by the health authorities. The records must be kept for at least 5 years after the date on which the study ends early or finally, and in accordance with local requirements. The investigator will keep the following exact, complete, and up-to-date records related to the investigator's participation in this study:

- All correspondence with the EC, Medtronic, monitors, and competent authorities, including the reports required related to this study
- Records of the subjects' clinical history
- Signed Subject Data Release Form documents
- All relevant complaints from subjects
- Observations regarding adverse episodes
- Clinical Investigation Plan and amendments
- All the CRFs and sets of data required by the Clinical Investigation Plan
- Signed clinical trial agreements
- Authorizations, renewals, and correspondence from the EC

